# Statistical Analysis

# **Analysis Sets:**

#### Intention-To-Treat (ITT) analysis set:

All enrolled subjects who received at least one dose of investigational product.

#### Modified Intention-To-Treat (mITT):

All enrolled subjects who received at least one dose of investigational product and have one post Baseline efficacy measurement.

#### General Statistical Methods:

All measured variables and derived parameters will be listed individually and, if appropriate, tabulated by descriptive statistics. Summary statistics will be provided for all safety, exploratory and Baseline/demographic variables. For categorical variables, frequency tables including percentages will be presented. For continuous variables, descriptive statistics such as number of available observations, mean, median, standard deviation, minimum and maximum will be tabulated. All available data and the tabulation of results will be displayed by initial dose level and with all levels pooled as a whole, if applicable.

The data will be analysed as described in the Statistical Analysis Plan.

## Safety Analysis:

Changes in vital signs and routine laboratory data will be presented with descriptive statistics to demonstrate the trend of change.

Number of subjects with physical abnormality at each scheduled visit will be tabulated by body system and by dose level. ECG examination results will be displayed in descriptive statistics and by dose level with number of subjects with abnormal findings tabulated for each schedule visit.

AE incidence will be summarised descriptively by system organ class (SOC), high level term (HLT) and preferred term (PT) using the latest version of Medical Dictionary for Regulatory Activities (MedDRA; current version 24.0) and by dose level and for the total population. The AEs severity grade, as determined by the latest version of the National Cancer Institute Common Terminology Criteria for Adverse Events (NCI-CTCAE; current version 5.0), and their relationship to study drug will be analysed by SOC, HLT and preferred term by dose level and for all subjects as a group. The action taken, and the outcome will also be analysed accordingly.

263		PRIVILEGED & CONFIDENTIAL
Investigational Product: AGI-134	A Phase I/IIa, multicentre, two-parts, open label study designed to evaluate the safety and tolerability of escalating	Protocol No. AGI-134.FIM.101
Phase: I/IIa	doses of AGI-134 in unresectable/metastatic solid tumours.	Version 6.1 31 May 2021

Statistical Analysis
-------------------------

10		PRIVILEGED & CONFIDENTIAL
Investigational Product: AGI-134	A Phase I/IIa, multicentre, two-parts, open label study designed to evaluate the safety and tolerability of escalating	Protocol No. AGI-134.FIM.101
Phase: I/IIa		Version 6.1 31 May 2021

#### 1 INTRODUCTION

#### 1.1 AGI-134

Humans, apes and Old World monkeys do not express the  $\alpha$ -1,3-galactosyltransferase ( $\alpha$ 1,3GT) enzyme, which catalyses the synthesis of alpha-Gal epitopes presented on cell surface glycolipids and glycoproteins in other mammals (U. Galili et al. 1988). Humans therefore recognise alpha-Gal epitopes as foreign and, through constant antigenic stimulation by commensal gut bacteria expressing alpha-Gal-like epitopes, produce anti-alpha-Gal antibodies (termed anti-Gal) in titres as high as 1% of total immunoglobulins throughout life (Galili 1984; Uri Galili et al. 1988; Posekany et al. 2002). When anti-Gal antibodies bind to alpha-Gal-bearing tissue, they activate the complement cascade, trigger complement-dependent cytotoxicity (CDC) and initiate antibody-dependent cellular cytotoxicity (ADCC), resulting in the release of inflammatory mediators and lysis of the tissue.

AGI-134 is designed to label cells with alpha-Gal, and by intratumoural administration, to target anti-Gal antibodies to cancer cells and trigger a systemic antitumour response. Preclinical pharmacology studies have shown that the synthetic glycophospholipid AGI-134 is incorporated into human cancer cell membranes, binds anti-Gal antibodies and induces CDC and ADCC, as well as phagocytosis by antigen presenting cells (APC). Taken together, APCs will have an increased uptake of tumour antigens which will then be cross-presented to effector T cells, to yield a systemic antitumour response. Indeed, animal model studies using galactosyltransferase knockout mice (GT KO) that can generate anti-Gal antibodies with grafted B16-F10 mouse melanoma, showed that treatment with AGI-134 leads to regression of established tumours and protects from secondary tumour development in a dose-dependent and an anti-Gal antibody-dependent manner.

For detailed background information refer to the AGI-134 Investigator's Brochure (IB)

#### 1.1.1 Nonclinical Studies

Nonclinical in-vitro studies of the mechanism of action (MoA) of AGI-134 have shown that AGI-134 incorporates into cell membranes, binds anti-Gal antibodies and induces ADCC and CDC, as well as phagocytosis by APCs. Complement-lysed cells, resulting from AGI-134 incorporation and exposure to serum, were specifically phagocytosed by human APCs and murine CD8 $\alpha$ + dendritic cells, which cross-presented a model antigen to CD8+ T cells.

GT KO mice that do not express the alpha-Gal sugar and can be induced to form anti-Gal antibodies by immunisation with pig kidney homogenate, were used for in-vivo studies of AGI-134. GT KO mice grafted with B16-F10 melanoma showed that intratumoural administration of AGI-134 resulted in primary tumour regression, improved survival and an abscopal effect that protected the mice from development of a distal secondary tumour. In addition, studies showed that a combination of AGI-134 and an anti-PD1 monoclonal antibody had a synergistic benefit in protection from secondary tumour growth.

Nonclinical pharmacokinetic, toxicokinetic and toxicity studies were conducted using animal species that lack alpha-Gal and express anti-Gal antibodies, so that potential effects induced by the interaction of the alpha-Gal portion of AGI-134 and anti-Gal antibodies could be observed.

10		PRIVILEGED & CONFIDENTIAL
Investigational Product: AGI-134		Protocol No. AGI-134.FIM.101
Phase: I/IIa		Version 6.1 31 May 2021

Relevant animal species include the Cynomolgus monkeys and the transgenic alpha-1,3-galactosyltransferase Knock Out mice.

The study in Cynomolgus monkeys, conducted under good laboratory practice (GLP), included administration of AGI-134 at dose levels of 10 mg/kg (SC) or 50 mg/kg (SC) and 2 mg/kg (IV) or 10 mg/kg (IV) once weekly for four weeks (total of five doses). The highest tested dose (50 mg/kg) is ~ 5-fold higher than the expected clinical dose (as per body surface). All doses were well tolerated. There were no AGI-134-related clinical signs, no AGI-134-related changes in haematology or coagulation and there were no definitive AGI-134-related changes in clinical chemistry or urinalysis parameters.

Based on the above results, the No observed Adverse Effect Level (NOAEL) was considered to be 50 mg/kg (SC) [Day 29  $C_{max}$  of 32,600 ng/mL and 27,600 ng/mL for males and females, respectively and an AUC(0-24) of 444,000 hr\*ng/mL and 360,000 hr\*ng/mL for males and females, respectively] and 10 mg/kg (IV) [Day 29  $C_{max}$  of 257,000 ng/mL and 253,000 ng/mL for males and females, respectively and an AUC(0-24) of 1,680,000 hr\*ng/mL and 1,260,000 hr\*ng/mL for males and females, respectively].

For detailed information refer to the AGI-134 IB.

#### 1.1.2 Clinical Trials

This is the first in human clinical study of AGI-134.

#### 1.2 STUDY RATIONALE AND DOSE SELECTION

The selection of the AGI-134 dose is based on the in-vitro and in-vivo efficacy studies in mice and safety studies in Cynomolgus monkeys.

Anti-Gal is a natural anti-carbohydrate antibody and, as such, has a relatively low affinity for alpha-Gal, compared to antibodies raised against peptide antigens. Where anti-peptide antibodies often have nM affinities for their single antigens, anti-Gal has an affinity of ~10  $\mu$ M for a single alpha-Gal antigen (Wieslander et al. 1990; Wang et al. 1999; Carlson et al. 2007). Hence, to drive the creation of immune complexes and subsequent complement-mediated cytolysis and antibody-dependent cell-mediated cytotoxicity, anti-Gal has to bind to the cells at a high density. To achieve a high cell surface density of anti-Gal, the surface of the tumour cells must be coated with a high density of AGI-134. When the cells are coated with AGI-134 in this way, the spatial arrangement of alpha-Gal on the cell surface drives multivalent antibody binding avidity, which increases the functional affinity of the anti-Gal IgG and IgM molecules from 10  $\mu$ M to 10 pM. Therefore, high cell surface density of alpha-Gal is required to bind anti-Gal with sufficient avidity to drive downstream effector functions. This is observed and recognised clinically when porcine tissue, which is highly alpha-Gal positive, is rapidly rejected by anti-Gal antibodies in humans (Geller et al. 1992).

The literature, as well as our data, suggest that, to be efficacious, AGI-134 must be injected into the tumour at a concentration that labels as many tumour cells as possible with a sufficient density of alpha-Gal to drive CDC, ADCC and subsequent uptake of tumour debris by APCs. By labelling the tumour cells with a high density of alpha-Gal, multivalent interactions between anti-Gal antibodies and alpha-Gal on the tumour cell surface are more likely, stabilising the binding of anti-Gal antibodies and initiating downstream effector functions.

20		PRIVILEGED & CONFIDENTIAL
Investigational Product: AGI-134		Protocol No. AGI-134.FIM.101
Phase: I/IIa		Version 6.1 31 May 2021

The concentration of AGI-134 that the tumour cells encounter will dictate the number of AGI-134 molecules that are inserted into the tumour cell membranes. We have demonstrated this in-vitro, where increasing the concentration of AGI-134 increases the molecule incorporation onto the cell membrane, the binding of anti-Gal, as well as increasing functional effect, measured by increased CDC.

For detailed information refer to the AGI-134 IB

In mice, we have demonstrated that increasing the concentration of AGI-134 improves the abscopal efficacy of the alpha-Gal glycolipid in a melanoma model in GT KO mice. Tumours were injected intratumourally with Phosphate Buffered Saline (PBS) (as mock treatment) or AGI-134, and development of the secondary tumour (which represents distant metastases) was monitored. When primary tumour was injected with 100 μL of AGI-134 in concentrations of 1, 5 and 10 mg/mL (total dose: 0.1-1 mg AGI-134), there was increasing efficacy at each concentration (see Section: Non-clinical Pharmacology in the IB). In a side-by-side comparison of using 10 mg/mL and the maximal feasible concentration (solubility-wise) of 25 mg/mL AGI-134, the two formulations had similar potent activity. In addition, AGI-134 in a concentration of 25 mg/mL administered intratumourally resulted in primary tumour regression and had a beneficial effect on survival (see Section: Non-clinical Pharmacology in the IB). In conclusion, 25 mg/mL concentration demonstrated compelling efficacy evidence in-vivo.

Given the above, while the minimal trough concentration to obtain the optimal functionality invivo is 10 mg/mL, as tumours in human are expected to vary in their chemical-physical propensities, the maximal feasible concentration will be used (25 mg/mL) for all doses with variable injection volumes. The clinical dose of AGI-134 injected into the tumour will be at a volume that is calculated based on the tumour dimensions, so that as much of the tumour as possible comes into contact with the injected solution.

The anticipated clinical dose range is 25-200 mg per injection (~0.4-3.3 mg/kg in a 60-kg individual). To support the safety of the clinical starting dose and selected dose range, repeated toxicity studies were performed in Cynomolgus monkeys. In order to maximise the opportunity to detect potential toxicities and to account for potential faster clearance in animals relative to humans, a once-weekly treatment schedule was employed. AGI-134 was well tolerated at all tested doses. At the NOAEL doses (50 mg/kg SC and 10 mg/kg IV, highest tested doses), systemic and local exposure was significantly beyond that anticipated clinically. The highest SC dose (50 mg/kg), is 40-fold higher than the anticipated starting dose (based on the human equivalent dose) and 120-fold higher on a weekly human equivalent dose basis. The 50 mg/kg SC is ~ 5-fold higher than the highest expected clinical dose.

The highest IV dose (10 mg/kg) is 8-fold and 24-fold the starting clinical dose on a per dose and weekly dose basis. This dose is expected to cover the highly vascularised nature of some solid tumour types and cover the risk encountered in the worst case of systemic exposure. Based on the 1/6th of the Highest Non-Severely Toxic Dose (HNSTD) approach to estimate a safe starting dose as outlined in ICH S9, the doses of 8.33 mg/kg (1/6th 50 mg/kg dose) and 1.67 mg/kg (1/6th 10 mg/kg) represent multiples of about 20- and 4-fold, respectively, compared with the proposed starting dose of 25 mg per subject. As such, the nonclinical toxicology studies support the selected starting dose and the dose range.

90		PRIVILEGED & CONFIDENTIAL
Investigational Product: AGI-134		Protocol No. AGI-134.FIM.101
Phase: I/IIa		Version 6.1 31 May 2021

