  - O Part 1: The total size of the tumour(s) should allow injection of the total volume required at each escalation cohort. The volume can be injected into one lesion or divided into more than one lesion, but the total volume should be given according to the total dose at each escalation part. When volume is divided between several tumours, at least 1 mL should be injected into each tumour.
  - o Part 2: Tumour dimensions should allow injection of a minimum of 1 mL.
- 8. Has  $\geq$  2 lesions
  - Has ≥1 injectable lesion which is amenable to injection and biopsy and is evaluable according to RECIST v1.1.
  - Has another lesion which is amenable for biopsy and is evaluable according to RECIST v1.1. Superficial large lesions of more than 25 cm can be considered as two lesions upon discussion with and approval by the Sponsor.
- 9. Evaluable Disease according to RECIST v1.1
- 10. Has an Eastern Cooperative Oncology Group (ECOG) Performance Status score of 0 or 1.
- 11. Has a life expectancy >3 months

		PRIVILEGED & CONFIDENTIAL
Investigational Product: AGI-134		Protocol No. AGI-134.FIM.101
Phase: I/IIa		Version 6.1 31 May 2021

- 12. Adequate organ function at Screening as defined below. All laboratory assessments should be performed within 10 days prior to treatment initiation.
  - o Haematology:
    - White blood cell (WBC)  $\geq 2,500/\text{mm}^3$
    - Absolute neutrophil count ≥ 1500 /mm^3
    - Platelet count  $\geq 100,000/\text{mm}^3$
    - Haemoglobin ≥9 g/dL or ≥5.6 mmol/L
    - Haematocrit >30%
  - Renal function:
    - Creatinine ≤1.5x Upper limit of normal (ULN) OR measured or calculated creatinine clearance (glomerular filtration rate [GFR]) can also be used in place of creatinine or CrCl) > 50 mL/min for subject with creatinine levels > 1.5x institutional ULN
  - o Hepatic function:
    - Total Bilirubin: ≤1.5xULN OR Direct bilirubin ≤ULN for subjects with total bilirubin levels >1.5xULN
    - AST (SGOT) and ALT (SGPT): ≤2.5xULN OR ≤5xULN for subjects with liver metastases
  - Coagulation
    - International Normalised Ratio (INR) or Prothrombin Time (PT): ≤1.5xULN unless subject is receiving anticoagulant therapy as long as PT or PTT is within therapeutic range of intended use of anticoagulants
    - Activated Partial Thromboplastin Time (aPTT): ≤1.5xULN unless subject is receiving anticoagulant therapy as long as PT or PTT is within therapeutic range of intended use of anticoagulants

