# 7.2.1 Definition of an Overdose for this Protocol and Reporting of Overdose to the Sponsor

An overdose in AGI-134 in humans cannot be defined as this is a first in human study.

In a GLP repeat-dose toxicology study in Cynomolgus monkeys, AGI-134 was well tolerated at doses exceeding the highest planned clinical dose (200 mg). The NOAEL was considered to be 50 mg/kg/dose (SC) (~5-fold higher than the highest expected clinical dose) and 10 mg/kg/dose (IV) (equivalent to the highest planned clinical dose that covers the highly vascularised nature of some solid tumour types and the risk encountered in the worst case of high systemic exposure).

No specific information is available on the treatment of an overdose of AGI-134. In the event of overdose, the subject should be observed closely for signs of toxicity. Appropriate supportive treatment should be provided if clinically indicated.

Refer to Safety Manual for Reporting of Overdose to Sponsor Instructions

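### Does Section 1.2 overstate the intravenous safety margin for the starting dose and the 200 mg top dose?

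*Combined protocol and SAP*

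**What the plan says.** Section 1.2 sets the scale of the clinical doses: "The anticipated clinical dose range is 25-200 mg per injection (~0.4-3.3 mg/kg in a 60-kg individual". It then gives multiples of the monkey NOAEL doses over the 25 mg start.

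- Subcutaneous: "The highest SC dose (50 mg/kg), is 40-fold higher than the anticipated starting dose (based on the human equivalent dose". The weekly figure is 120-fold, and against the highest clinical dose it is about 5-fold. Section 1.1.1 puts the 5-fold figure on a body-surface basis.
- Intravenous: "The highest IV dose (10 mg/kg) is 8-fold and 24-fold the starting clinical dose on a per dose and weekly dose basis". Section 1.2 gives no intravenous multiple against the highest clinical dose.

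Next comes the one-sixth check (8.33 mg/kg subcutaneous, 1.67 mg/kg intravenous), whose results "represent multiples of about 20- and 4-fold, respectively, compared with the proposed starting dose of 25 mg per subject". No basis is named for the 20 and the 4.

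On exposure at both NOAEL doses, the section says: "50 mg/kg SC and 10 mg/kg IV, highest tested doses), systemic and local exposure was significantly beyond that anticipated clinically". It closes: "As such, the nonclinical toxicology studies support the selected starting dose and the dose range".

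Section 7.2.1 returns to the NOAELs when it discusses overdose, and describes the intravenous one as "10 mg/kg/dose (IV) (equivalent to the highest planned clinical dose". Both sections use the intravenous dose to cover the worst case of systemic exposure from a highly vascularised tumour.

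**The concern.** Two things catch the eye. First, the multiples just before the one-sixth check are labelled per dose and weekly, while the check itself has no label. A reader who divides the per-dose 8-fold by six gets 1.3, not 4, and may take the printed figure for an error that flatters the starting dose.

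Second, 200 mg is eight times 25 mg. An intravenous dose that is 8-fold the start is therefore only level with the top dose, as Section 7.2.1 says. Yet Section 1.2 speaks of exposure well past the clinical level at both NOAEL doses and concludes that the whole dose range is supported, giving a top-dose multiple for the subcutaneous route only.

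This is a first-in-human study, and the intravenous arm is the plan's cover for the worst case. If the rationale really contradicted itself, investigators and ethics committees would be working from a margin that the data do not give.

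**Working it through.** **Inputs.** Doses of 25 and 200 mg, a 60-kg subject, NOAELs of 50 mg/kg SC and 10 mg/kg IV, and the multiples 40, 120, 5, 8 and 24, from Section 1.2. The monkeys were dosed weekly (Section 1.1.1) and subjects every three weeks (Section 3), so the weekly factor is 3.

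**Step 1: reproduce the plan's multiples.** The start is 25/60 = 0.417 mg/kg and the top is 200/60 = 3.33 mg/kg. The monkey-to-human divisor implied by the plan is 50/(40 × 0.417) = 3.0 for SC and 10/(8 × 0.417) = 3.0 for IV. With 3.0:

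- SC: (50/3)/0.417 = 40; weekly 3 × 40 = 120; at 200 mg (50/3)/3.33 = 5.0
- IV: (10/3)/0.417 = 8; weekly 3 × 8 = 24

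All five agree with the text.

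**Step 2: the one-sixth check on each available scale.**

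| Scale | SC | IV |
|---|---|---|
| Printed | 20 | 4 |
| Per-dose human equivalent | 40/6 = 6.7 | 8/6 = 1.33 |
| Weekly human equivalent | 120/6 = 20 | 24/6 = 4 |
| Unconverted mg/kg at 60 kg | 8.33/0.417 = 20 | 1.67/0.417 = 4 |

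The printed figures match two of the three scales exactly. Those two coincide because the divisor of 3 for species and the factor of 3 for schedule cancel, so the text cannot tell us which was meant. What is missing is a label. The lowest value on any scale is 1.33, so at 60 kg the starting dose stays below the one-sixth equivalent however it is read.

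**Step 3: intravenous NOAEL against 200 mg.** Per dose: 8 × 25/200 = 1.0. Weekly: 24 × 25/200 = 3.0. The per-dose value is what Section 7.2.1 calls equivalent. Section 1.2 prints no other figure, so there is no numerical conflict between the two.

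**Step 4: dose against exposure.** The sentence in Section 1.2 is about systemic and local exposure; the one in Section 7.2.1 is about dose. The only exposure data in the protocol are the Day 29 monkey values in Section 1.1.1:

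- AUC, IV over SC: 1,680,000/444,000 = 3.8 (males); 1,260,000/360,000 = 3.5 (females)
- Cmax, IV over SC: 257,000/32,600 = 7.9 (males); 253,000/27,600 = 9.2 (females)

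One fifth of the dose gave several times the exposure when given intravenously. Dose multiples therefore do not carry over to exposure across routes. The protocol gives no predicted human Cmax or AUC after intratumoural injection, so the exposure sentence can be neither confirmed nor refuted from it.

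**The case for a change.** The strongest case for a change concerns body weight. Part 1 doses are flat in mg: "the total volume should be given according to the total dose at each escalation part". The multiples are worked for 60 kg, and Sections 4.1 and 4.2 set no weight limit. If the human-equivalent dose is held constant per kg, the per-dose one-sixth intravenous multiple is 1.33 × W/60 = W/45, and the 200 mg multiple is W/60. The first falls below 1 under 45 kg and the second under 60 kg (0.83 at 50 kg). On the printed 4-fold scale the one-sixth threshold would be 4 × W/60 = W/15, or 15 kg, which is irrelevant for adults. On this view the unnamed basis decides whether the check holds for every eligible adult.

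The arithmetic is right, but the thresholds rest on an assumed linear scaling with weight, whereas Section 1.1.1 works by body surface. With weight to the power 2/3 (also an assumption), the one-sixth threshold moves to 60 × (1/1.333)^1.5 = 39 kg, and the 200 mg value at 50 kg becomes (50/60)^(2/3) = 0.89. In Part 2 the dose follows tumour dimensions, with the RP2D as a ceiling, so it is not flat. The one-sixth rule is invoked for the starting dose only; higher doses are reached stepwise, with Safety Committee review after the first cycle at each level.

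Nor does a multiple near 1 mean toxicity is near. The intravenous NOAEL was the highest intravenous dose tested and was well tolerated, so it sets a lower limit on where toxicity begins. It does not demonstrate a margin above 200 mg either.

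Three points stand: the 20 and 4 have no stated scale, Section 1.2 leaves the intravenous figure at 200 mg to Section 7.2.1, and the exposure sentence is not quantified in the protocol.

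**Conclusion.** Neither a contradiction nor an overstated margin is shown. The printed 20 and 4 are correct on two scales and lack only a label; the per-dose human-equivalent values are about 6.7 and 1.3. The intravenous multiple at 200 mg is about 1.0 per dose and 3.0 weekly. It is disclosed in Section 7.2.1 and follows from Section 1.2 by one division. If the 8-fold figure is itself rounded (7.5 to 8.5), the per-dose values run from 1.25 to 1.42 for the one-sixth check and from 0.94 to 1.06 at 200 mg, which changes nothing in the reasoning.

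These results rest on the plan's 60-kg subject and its implied divisor of 3.0. The exposure sentence remains unquantified in the protocol, which refers to the Investigator's Brochure for detail.

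An amendment would label and repeat figures in a background section. No dose level, escalation step, DLT rule, eligibility criterion, endpoint or sample size is computed from them, so the trial would run and be analysed identically. A sponsor revising Section 1.2 for other reasons could add the label in passing, but this point alone calls for no change.
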